### **The geriatric parameters are:**

#### **1) Co-morbidity (Self questionnaire and Team)**

To assess the co-morbidity of each patient, the following items will be documented:

- Existence of one or more hospitalizations in the last 12 months for a reason other than cancer management.
- Updated Charlson score (15)

## **2) Functional status**

### **a) Activities of daily living (Self questionnaire)**

The self-administered questionnaire replicating the items of the Katz index (16) will be used to measure basic activities of daily living (ADL). Thus, the ADL score for each patient can range from 0 (unable to perform any activity) to 6 (able to perform all activities). Disability in a BDA is defined as the need for assistance with at least one activity of daily living.

Threshold value: <6

### **b) Instrumental activities of daily living (IADL) (Self questionnaire)**

The self-administered questionnaire reproducing the IADL items will be used to measure instrumental activities of daily living (IADL) (17). Disability in an IADL is defined as the need for assistance to complete at least one IADL. The denominator will be adjusted to account for patients not performing certain activities listed in the IADL.

The threshold value is: <14 when the patient does or did all IADL activities. A score lower than 14/14 is considered pathological (e.g., if the patient needs help with housework and managing money, the score will be 12/14 and therefore pathological). If the patient has never done certain activities, the score is adjusted according to the denominator corresponding to the maximum number of points possible on the activities performed by the patient (e.g.: if the patient has never done housework, the score will be 12/12, and the IADL is considered normal).

### **c) Eastern Cooperative Oncology Group Functional Index (ECOG-PS) (Case report)**

The ECOG is a five-point scale designed to measure the level of interference of symptoms with normal activity and the number of hours awake in bed (18). An ECOG  $\geq 2$  is considered a decrease in functional status.

Threshold value = ECOG  $\geq 2$

## **3) Mobility (Self questionnaire and Team questionnaire)**

To assess mobility, the unipodal station test (19) and the number of falls reported in the last 6 months (or last 2 months at follow-up) will be used. The unipodal station test is considered abnormal if the patient is unable to balance on one leg for more than 5 seconds or if the patient has had a fall in the last 6 months.

Threshold value: monopodal support < 5 seconds or fall in the last 6 months (and in the last 2 months for follow-up)

Volunteer centers will also measure the 4-meter walking speed (TM-4) (20). The TM-4 is done over a distance of eight meters including the two meters of acceleration and deceleration. The time is measured for the central 4 meters, to avoid acceleration and deceleration at both ends of the course. Precise instructions will be given to the patient: "walk at your usual pace, at your ease". The test will be repeated twice. A 4 m walking speed test longer than 4 seconds is considered as pathological (21).

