## 8. PATIENT MONITORING

### 8.1 during treatment :

- Clinical examination: weight, height, BP, collection of toxicities and clinical tumor assessment

- Cycle 1 and 2: at D1, D7 and D14
- Cycles 3 and following: at D1 of each cycle
- At the end of treatment visit

The ECOG is completed on Day 1 of each cycle (cycle 1 and following) and at the end-of-treatment visit.

- Bioassay:

At each cycle: at D1 and D14; (for cycle 1, the biological test at D1 can be the inclusion test, if it is less than 14 days old).

The assessment at Day 1: CBC-platelets, natraemia, kalemia, calcemia, magnesemia, phosphoremia, uricemia, creatininemia, creatinine clearance, albuminemia, ASAT, ALAT, PAL, total and conjugated bilirubinemia, GGT, TP, TSH, lipase, INR for patients treated with AVK.

Assessment at D14: CBC/blood platelets, creatinine clearance, natraemia, kalemia, creatinine, ASAT, ALAT, PAL, total and conjugated bilirubin, GGT, INR for patients treated with AVK.

- At the end-of-treatment visit: CBC/blood platelet count, natraemia, kalemia, creatinine, creatinine clearance, AST, ALT, PAL, total and conjugated bilirubin, GGT

A coagulation test should be performed at D1 and D14 of each cycle, if patients are treated with anticoagulant. If the values are outside the therapeutic range, the dose of anticoagulant should be modified and a coagulation test should be performed every week until stabilization.

- Other follow-up:

During treatment, an ECG will be performed if deemed useful by the investigator.

Every 4 weeks, until progression, CEA measurement will be performed as well as quality of life and geriatric parameters assessment.

Every 8 weeks, until progression, a thoraco-abdomino-pelvic scan will be performed to evaluate the tumor response.

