## **11.2 Exploratory evaluation of geriatric parameters**

It is recommended that each patient has had a geriatric consultation prior to inclusion.

An exploratory analysis is planned to look for geriatric prognostic factors for the primary endpoint. An analysis of the evolution of geriatric parameters during the follow-up will also be performed.

The "patient" self-questionnaire including the collection of activity of daily living and the "team" questionnaire including the quality of life (Spitzer QoL Index) will be completed at inclusion and at each evaluation (every 4 weeks).

The self-questionnaire will be completed by the patient. The "team" questionnaire will be completed by a clinical research associate, a nurse or the investigator depending on the organization of the service.

The 2 questionnaires include the assessment of geriatric parameters with the following domains: functional status, mobility, cognition, depression, energy, social context and quality of life; physical activity, nutrition, hearing and vision will only be completed at inclusion. A cut-off value is determined for each domain.

The questionnaires and self-questionnaires are presented in Appendices 2 and 3. These evaluation questionnaires have been used in onco-geriatrics, particularly as self-questionnaires (10-14).

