## Exploratory analysis

In an exploratory way, in order to study the temporal evolution of geriatric and quality of life scores (Spitzer QoL Index, IADL, ...), mixed models of analysis of variance for repeated measures of each of the scores will be performed.

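### The mobility flag counts falls over 6 months at inclusion but over 2 months at follow-up, so comparison with baseline shows an improvement even when the fall rate is constant

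*Protocol*

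**What the plan says.** Protocol section 11.2, item 3 (Mobility), combines a one-leg stand test with a fall history. On falls, "the number of falls reported in the last 6 months (or last 2 months at follow-up) will be used". The cut-off is an either/or rule: a one-leg stand under 5 seconds, or a "fall in the last 6 months (and in the last 2 months for follow-up". Another sentence of the same item calls the test abnormal on the 6-month window alone, with no exception for follow-up.

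The opening of section 11.2 says that the two questionnaires "will be completed at inclusion and at each evaluation (every 4 weeks"). Section 8.1 gives the same 4-week rhythm until progression, and the examination schedule marks the questionnaires on day 1 of each cycle and also in the 8-weekly column. Mobility is among the repeated domains: "functional status, mobility, cognition, depression, energy, social context and quality of life; physical activity, nutrition, hearing and vision will only be completed at inclusion".

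On use, section 11.2 states: "An analysis of the evolution of geriatric parameters during the follow-up will also be performed". Section 11.4 (Exploratory analysis) plans repeated-measures mixed models "in order to study the temporal evolution of geriatric and quality of life scores", naming the Spitzer index and IADL and leaving the list open. SAP sections 1.1.3 and 4.6.2 carry the same intentions. Neither document rescales falls to a common period, leaves baseline out of the comparison, or says how the mobility flag is derived at follow-up.

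**The concern.** A flag that is triggered by any event in a look-back period is triggered less often when the period is shorter. Here the period shrinks by a factor of three between inclusion and the first follow-up questionnaire. A change from baseline in this flag therefore mixes any real change in mobility with a change of definition. The definitional part always points the same way, towards fewer abnormal patients once treatment has begun.

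Protocol section 1.2 says that the study is meant to describe regorafenib in elderly patients, geriatric parameters included. A table or model comparing follow-up with baseline could suggest that mobility is preserved or improved on treatment, or could offset a real decline. The effect is a single step at the first follow-up visit. Later visits share one definition and are comparable with each other.

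**Working it through.** The documents give no fall rate and no share failing the one-leg stand, so there is no plan figure to reproduce. Both are assumptions below and are varied over a range.

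**Inputs from the documents.** Fall window of 6 months at inclusion and 2 months at follow-up (Protocol 11.2, item 3). Questionnaires every 4 weeks, i.e. 28 days (Protocol 8.1 and 11.2). One month = 30.4375 days (SAP 3.2).

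**Step 1: fall component alone.** At a constant rate r per month (Poisson), the probability of at least one fall in m months is 1 − exp(−m·r).

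| Assumed r | Baseline, 1 − exp(−6r) | Follow-up, 1 − exp(−2r) |
|---|---|---|
| 0.03 | 1 − exp(−0.18) = 16.5% | 1 − exp(−0.06) = 5.8% |
| 0.05 | 1 − exp(−0.30) = 25.9% | 1 − exp(−0.10) = 9.5% |
| 0.10 | 1 − exp(−0.60) = 45.1% | 1 − exp(−0.20) = 18.1% |

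**Step 2: the composite flag.** Let P6 and P2 be the probabilities of a fall in 6 and 2 months, and b the share failing the stand, taken as independent of falls and constant over time. The share flagged is b + (1 − b)P, so the spurious drop is (1 − b)(P6 − P2). At a constant rate, P2 = 1 − (1 − P6)^(1/3). With P6 = 30%, P2 = 1 − 0.70^(1/3) = 11.2%.

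| Assumed b | Flagged at baseline | Flagged at follow-up | Spurious drop (points) |
|---|---|---|---|
| 0% | 30.0% | 11.2% | 18.8 |
| 20% | 44.0% | 29.0% | 15.0 |
| 40% | 58.0% | 46.7% | 11.3 |
| 60% | 72.0% | 64.5% | 7.5 |

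With P6 between 10% and 50% and b between 0 and 60%, the drop runs from 2.6 points (P6 = 10%, b = 60%) to 29.4 points (P6 = 50%, b = 0). If patients who fail the stand also fall more often, the drop is smaller at the same overall P6, because only falls among those who pass can change the flag.

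**Step 3: clustered falls.** With a negative binomial count (dispersion k = 0.5, an assumption), the six-month mean is μ6 = k[(1 − P6)^(−1/k) − 1] and P2 = 1 − (1 + μ6/(3k))^(−k). For P6 = 30%, μ6 = 0.520 and P2 = 13.8%. The fall component still drops by 16.2 points instead of 18.8.

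**Step 4: overlap with baseline.** Two months is 2 × 30.4375 = 60.875 days. If the first follow-up questionnaire comes 28 days after the baseline one, its window reaches 60.875 − 28 = 32.9 days before baseline, so a fall already counted at inclusion can be recorded again. The baseline questionnaire may precede inclusion by up to 14 days (Protocol 4) and treatment may start up to 7 days after inclusion (Protocol 5). At the extreme, the gap to day 1 of cycle 2 is 14 + 7 + 28 = 49 days and the reach is 60.875 − 49 = 11.9 days. The overlap shrinks but remains.

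**The case against.** The shorter window is stated openly and has a plausible reason: a 6-month look-back at an early follow-up visit would mostly cover time before treatment. Two months also fits the 8-weekly column of the schedule. Mobility is not named in the planned mixed models, which speak of scores, whereas this is a yes/no flag. The analysis is exploratory, in a trial sized at 42 patients. Much of this stands. A long fall history is sensible for baseline screening, and some change of window is defensible. What is missing is a convention for comparing follow-up with baseline, and the general commitment to analyse the evolution of geriatric parameters covers mobility. Using only 8-weekly visits would not remove the 6-versus-2-month mismatch.

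A reader might infer two stronger things that the documents do not support.

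- *That the percentages in Step 1 are the shares flagged.* They are so only if nobody fails the one-leg stand. Step 2 gives the diluted figures for the flag itself.
- *That each fall is counted about twice and distorts the results.* The ratio 60.875/28 = 2.17 suggests it, but a double count needs at least two later questionnaires. With falls spread evenly over follow-up, the mean is 1.50 entries per fall with two follow-up questionnaires and 1.95 with six; with one it is 1. Protocol 1.2 cites a median treatment duration of 7.1 weeks in patients over 65, so, if exposure here is similar, many patients may have only one or two. Moreover, no planned analysis adds falls across visits. A rolling window of constant length makes neighbouring visits correlated but does not create a trend between them. Only the overlap with the baseline window matters, as a secondary point.

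**Conclusion.** The point holds as a minor one. As written, the flag builds in an apparent improvement between inclusion and follow-up when nothing has changed. For the composite it is about 7.5 to 19 points at an assumed six-month fall prevalence of 30%, and 2.6 to 29.4 points over the wider range tried. The direction follows from the documents' own windows. The size rests on assumptions about the fall rate, the share failing the stand, and the independence of the two. That the artefact would hide a real decline is possible but not shown, since no particular comparison of this flag with baseline is specified.

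The tumour control endpoint, overall and progression-free survival, time to IADL decline, time to Spitzer decline and the use of baseline mobility as a prognostic factor are all untouched, as are the one-leg stand and walking-speed tests taken alone.

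**What to change.** Add a derivation rule to SAP section 4.6:

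- In the analysis of change over time, define the mobility flag by the one-leg stand alone at every visit.
- Report falls separately as a rate per month: baseline count / 6 and follow-up count / 2. If the 2-month item stays, use only the 8-weekly questionnaires for falls. Successive windows then overlap by only 60.875 − 56 = 4.9 days.
- If the form can still be changed, ask at follow-up about falls since the last questionnaire and divide by the months elapsed. Each on-study fall then enters one questionnaire.
- Keep the 6-month definition for baseline description and prognostic models, and reconcile the sentence in the mobility item that gives no follow-up exception.

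The rate needs a count. The protocol text refers to the number of falls, but the questionnaires themselves were not in the text reviewed. If only yes/no is recorded, describe falls across follow-up visits and leave baseline out of that trend.

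The cost is a little derivation work, plus fewer follow-up time points for falls if the 2-month item is kept. SAP section 1.6 allows adjustments before the database is frozen.

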## **4) Nutrition**

### **a) Body Mass Index (Observation Booklet)**

The body mass index (BMI) will be calculated for each patient as follows:  $BMI = \text{Weight (Kg)} / [\text{Height (m)}]^2$ . BMI is an index commonly used to classify overweight and obesity in adults. The World Health Organization (1998) classifies normal weight with a BMI of 18.5 to 24.9 kg/m^2, overweight with a BMI between 25 and 29.9 kg/m^2, and obese with a BMI >

30 kg/m^2 . A BMI < 18.5 kg/m^2 is considered underweight and indicates severe malnutrition (22). A BMI < 21 already indicates undernutrition (HAS 2007) in the elderly.  
Threshold value in geriatrics: BMI < 21 kg/m^2

**b) Mini nutritional evaluation (Team Questionnaire)**

The Mini Nutritional Assessment (MNA-SF) is a 6-item questionnaire to detect malnutrition. These items are already collected in the G8 Mini Assessment. Patients are considered at risk of malnutrition if they have a score ≤ 11 out of a total of 14 (23).

Threshold value: score ≤ 11

The G8 scale used in the ONCODAGE study will be evaluated (5).

**c) Evaluation of weight loss by losing 4kg in 1 year (Self questionnaire)**

[figure not shown]
"In the past year, have you involuntarily lost more than 10 pounds?" (20)

**5) Cognition (Team Questionnaire)**

The Mini-COG will be used to detect cognitive impairment (24).

Scores:

- If 3-word recall = 0 positive test for cognitive impairment
- If the 3 words recall = 1 or 2
  - Either normal clock test: negative test for cognitive impairment
  - Either abnormal clock test: positive test for cognitive impairment
- If recall of 3 words = 3, negative test for cognitive impairment

**6) Depression (Self questionnaire)**

The 4-item Geriatric Depression Scale (mini GDS) is used to suspect depression. A score of 1 or higher indicates possible depression (25).

Threshold value:  $\geq 1$

### **7) Energy (Self questionnaire)**

A visual analog scale will be used to assess the energy domain (26). A score  $< 3$  indicates a positive fragility marker for this domain.

Threshold value:  $< 3$

### **8) Physical activity (Team Questionnaire)**

The validated self-questionnaire derived from the Canadian Study of Health and Aging Risk Factor Questionnaire (RFQ) will be used (27). Physical activity will be stratified according to 4 levels of exercise that are scored from 1 to 4 :

4- high level of exercise (more intense than walking at least 3 times a week)

3- moderate exercise (walking 3 times a week)

2- low level of exercise (either walking or more intense than walking, less than 3 times a week or exercise less intense than walking, any frequency)

1- No physical exercise

No exercise or low level of exercise (score 1 or 2) indicates a positive fragility marker for this domain.

Threshold value:  $\leq 2$

### **9) Social context (Self questionnaire)**

No reference tool yet exists to measure social context in gerontological research. The following question was chosen: *Will you have someone to care for you during the treatment period? If so, who is it?* (Spouse, children, friends, neighbors, caregivers).

Threshold value: no

### **10) Quality of life (Team Questionnaire)**

The Spitzer QoL Index questionnaire will be used to assess quality of life (9).

### **11) Hearing (Self questionnaire)**

The next question will be asked "do you have difficulty hearing or do you have a hearing aid?"

Threshold value: yes

### **12) Vision (Self questionnaire) (28):**

The following questions will be used:

Question 1: "Are you able to read a sentence in the newspaper (with or without glasses)?"

If no to question 1:

Question 2: "Can you read the headlines in the newspaper?"

Threshold value: answer no to question 1

## **11.3 Calculation of the number of subjects required**

The clinical assumptions are based on data from the CORRECT study and are as follows:

$H_0$  : A tumor control rate at 2 months after the start of treatment of 25% or less is not sufficient

$H_1$  : A tumor control rate at 2 months after the start of treatment of more than 25% is considered sufficient. A rate of 47% is expected.

With a one-sided  $\alpha$  risk of 5% and 90% power, 42 patients are required.

Patients who discontinue the study prior to documented tumor progression at 2 months will be considered non-responders for the primary endpoint analysis.

The decision rules after inclusion of 42 patients are:

If 15 or fewer patients show a complete or partial response or stability, then the treatment will be considered not effective.

If 16 or more patients have a complete, partial or stable response, then the treatment is considered effective.

A recruitment of 2 patients per month is planned.

## **11.4 Statistical analysis**

### **Populations of analysis**

All analyses will be done on an intention-to-treat basis on all included patients who have taken at least one treatment tablet.

### **Descriptive analyses**

Continuous variables will be described using mean, standard deviation, median, minimum and maximum, and interquartile range (Q1-Q3).

Qualitative variables will be described using frequencies and percentages. The percentages will be calculated without taking into account the missing modality.

### **Analysis of the judging criteria**

Censored data will be estimated and plotted using the Kaplan Meier (KM) method. Survival times will be described by medians and rates at different time points with their 95% confidence intervals. The median follow-up time will be calculated using the so-called "reverse Kaplan Meier" method.

### **Tolerance analysis**

Toxicities will be described, by the number of patients and toxicities according to the different grades and the different SOC. They will also be described by grouping grades 1-2 versus 3-4-5.

### **Analysis of geriatric parameters**

An analysis of prognostic factors for overall survival and progression-free survival will be performed. These analyses will be performed using univariate and multivariate Cox models.

The geriatric parameters and the inclusion variables considered clinically relevant will be studied in univariate. Variables that are significant at the 20% threshold can be introduced into the multivariate models. Several multivariate models can be constructed, and the comparison of the different models obtained will be carried out according to a measure of model adequacy (AIC), a measure of calibration (O'Quigley's  $R^2$ ) and a measure of accuracy (Breier score).

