4.6 Exploratory analyses

4.6.1 Definition

The exploratory analysis will investigate the predictive factors for response, overall survival, and progression-free survival with regorafenib therapy.

Prior to any inferential analysis, descriptive statistics of the predictive factors will be performed to assess the feasibility of this analysis.

The variables for which the p-value is lower than 0.20 in univariate analysis or judged clinically relevant among the list to be defined will be retained for the multivariate analysis. The prognostic factors studied will be the geriatric parameters.

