4.6.2 Evaluation

For univariate and multivariate analyses, hazard ratios will be estimated using a Cox model (Cox, 1984). The proportionality of the rates will be tested using the graphical representation and the test based on Schönfeld's residuals (Grambsch, 1994); the linearity of the effect of the continuous variables on the risk will be assessed from the graphical representation of the martingale residuals. Confidence intervals for the coefficient estimates of the Cox models will be calculated using the Wald method.

Several multivariate models can be constructed. The comparison of the different models obtained will be carried out according to a measure of adequacy of the model (AIC), a measure of calibration (O'Quigley's R^2) and a measure of accuracy (Breier score).

In an exploratory way, in order to study the temporal evolution of geriatric and quality of life scores (Spitzer QoL Index, IADL, ...), mixed models of analysis of variance for repeated measures of each of the scores will be carried out.

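### The planned calibration measure for comparing Cox models, O'Quigley's R², measures explained variation, so calibration is not assessed separately and no rule says which measure prevails

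*Protocol*

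**What the plan says.** Protocol 11.4 (Analysis of geriatric parameters) plans univariate and multivariate Cox models for overall and progression-free survival. On entry of variables it says "Variables that are significant at the 20% threshold can be introduced into the multivariate models". SAP 4.6.1 keeps the same threshold and adds a second route: "The variables for which the p-value is lower than 0.20 in univariate analysis or judged clinically relevant", from a list still to be drawn up.

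Both documents expect more than one final model. The Protocol says "Several multivariate models can be constructed", and SAP 4.6.2 says the same. The models are then compared on three properties, in nearly identical words. The Protocol has "a measure of model adequacy (AIC), a measure of calibration" and the SAP has "a measure of adequacy of the model (AIC), a measure of calibration". In each, O'Quigley's R² follows in brackets as the calibration measure (SAP: "a measure of calibration (O'Quigley's R^2"), and the Brier score, spelled Breier, is the measure of accuracy.

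The only other model checks, in SAP 3.5 and 4.6.2, are for proportional hazards and for linearity of continuous effects. Neither document plans a calibration slope, a comparison of predicted with observed survival, or internal validation. Neither says which form of O'Quigley's R² is meant, at what time the Brier score is taken, whether it is corrected for optimism, or which measure decides if the three disagree.

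**The concern.** Calibration is the agreement between the survival that a model predicts and the survival that is observed. O'Quigley's R² measures how much of the variation, or randomness, in the outcome the covariates explain. A model can explain a large share of the variation in the patients it was fitted to and still give predictions that are too extreme for new patients. One of the three stated criteria therefore does not measure the property it is named for.

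The setting makes this matter. The trial has 42 patients. Protocol 11.2 lists 12 numbered geriatric domains, some with several items, and clinically relevant inclusion variables are added to these. If 12 candidates had no prognostic value, 12 × 0.20 = 2.4 would still be expected to pass the screen by chance. Overfitting is thus the likely failure, and it spoils calibration while raising explained variation. A report that follows the plan would offer an R² value as its evidence on calibration. The analysis also answers a listed secondary objective, on geriatric prognostic and predictive parameters (Protocol 2.2, SAP 1.1.2).

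**Working it through.** **Inputs from the documents.** 42 patients, and success if at least 16 have tumour control (Protocol 11.3, SAP 1.4). This figure reproduces with the exact binomial: P(X ≥ 16 | 42, 0.25) = 0.0416 and P(X ≥ 16 | 42, 0.47) = 0.906, which meets 5% one-sided and 90%. It is used here only as the size of the dataset. The documents give no value for R², calibration, the Brier score or the number of events.

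**Step 1: how each measure reacts to a noise variable.** In its likelihood form, R² = 1 − exp(−LR/e), where LR is the likelihood-ratio statistic against the null model and e the number of events. AIC = −2·logL + 2k for k covariates. For nested models fitted to the same patients, adding a covariate cannot lower LR, so this R² cannot fall. AIC improves only if LR grows by more than 2. A pure noise covariate adds about 1 to LR on average, so it typically raises R² and worsens AIC.

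The number of events is an assumption. For six pure noise covariates, R² ≈ 1 − exp(−6/e):
- e = 42 (every patient has an event): 0.13
- e = 35.5: 0.16
- e = 30: 0.18

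**Step 2: simulation A.** 200 trials of 42 patients were simulated, with 10 standard normal covariates. Two were prognostic (log hazard ratios 0.5 and 0.4) and eight were noise. Survival was exponential with baseline mean 8 months, and censoring uniform over 12 to 24 months, giving 35.5 events on average. All settings are assumptions. Nested models of 1 to 10 covariates were fitted. The slope and the second Brier score were taken in 2000 new patients per trial.

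| Mean over trials | 2 covariates | 10 covariates |
|---|---|---|
| R², likelihood form | 0.303 | 0.465 |
| R², Schoenfeld-residual form | 0.313 | 0.455 |
| Calibration slope, new patients (ideal 1) | 0.93 | 0.36 |
| 6-month Brier score, fitting data | 0.197 | 0.174 |
| 6-month Brier score, new patients | 0.219 | 0.258 |

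Check against Step 1: R² = 0.303 with 35.5 events means LR = −35.5 × ln(0.697) = 12.8. Eight noise covariates add about 8, so R² ≈ 1 − exp(−20.8/35.5) = 0.44, near the simulated 0.465. AIC then worsens by about 16 − 8 = 8.

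**Step 3: what happens if one measure decides (simulation A).**

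| Deciding measure | Mean covariates chosen | Chose the worst-calibrated model |
|---|---|---|
| R², likelihood form | 10.0 | 61.5% |
| Brier score, fitting data | 8.4 | 34% |
| AIC | 2.9 | 3.5% |
| Brier score, new patients | 2.3 | 1.5% |

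The likelihood form never fell when a covariate was added. The residual form fell in about 27% of steps (100% − 72.7%).

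**Step 4: simulation B.** 600 trials of 42 patients were simulated with one true binary factor (HR 2.0) and censoring uniform over 12 to 33 months. Going from 1 to 3 to 6 variables, median R² rose 0.10, 0.15, 0.22 and the slope in new patients fell 0.93, 0.58, 0.34. In a rerun with an assumed median survival of 7 months, AIC chose the true one-variable model in 79% of trials and the six-variable model in 7%. With three true factors (HR 1.65 each), adding three noise variables moved R² from 0.19 to 0.26 and the slope from 0.65 to 0.42; AIC chose the six-variable model in 18%.

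**Step 5: does the Brier score carry calibration?** With discrimination held fixed and the log-odds of the predictions multiplied by 1, 2 and 3, the Brier score was 0.200, 0.212 and 0.228. The rises of about 0.012 and 0.029 match the miscalibration term (0.012 and 0.029). It does respond to calibration, but mixes it with discrimination.

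**The case against.** The strongest defence is that R² is one of three criteria and the other two do relevant work. AIC is listed first and penalises size. The Brier score contains a calibration component (Step 5). No rule makes R² decisive. The fall in slope comes from forcing noise variables into small models and would occur whatever R² were called. The simulations leave out the p < 0.20 screen and the feasibility step of SAP 4.6.1. The aim is to find prognostic factors reported as hazard ratios, for which calibration of absolute risk is secondary.

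Much of this stands, and it rules out four stronger readings that a reader might infer.
- That R² rises with every added variable. This holds only for the likelihood form, in nested models on the same patients. The documents specify neither the form nor nesting.
- That calibration is never assessed. The Brier score captures part of it.
- That the worst-calibrated model will be chosen. This requires R² or an uncorrected Brier score to outweigh AIC, and nothing in the plan says so.
- That survival predictions for frail patients would be given false support. Neither document plans such predictions or a risk score.

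The defence does not repair the label, since no form of this R² measures calibration. The Brier score is only partial cover: on the fitting data it improved from 0.197 to 0.174 while it worsened from 0.219 to 0.258 in new patients. As written, two of the three measures can favour an overfitted model, and the plan is silent on a conflict.

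**Conclusion.** The concern holds as a minor point. Both documents name as the calibration measure a statistic that does not measure calibration, and neither provides a separate one. Under the assumed settings, R² rose by about half (0.30 to 0.47) while the calibration slope fell from 0.93 to 0.36. Simulation B, with different assumptions, goes the same way. AIC largely contains the problem if it decides, but that is left open.

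The label error rests on definitions alone. The sizes rest on assumed effects, follow-up and numbers of covariates, and show what happens if one measure decides, not the full planned procedure. The consequence is confined to exploratory prognostic models. The primary endpoint and its decision rule are untouched.

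**What to change.** In Protocol 11.4 and SAP 4.6.2:

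1. Relabel O'Quigley's R² as a measure of explained variation, state which form is used, and make it descriptive only, not a basis for choosing between models of different size.
2. Name a bootstrap optimism-corrected calibration slope as the calibration measure. Each resample should repeat the whole selection, including the p < 0.20 screen.
3. Compute the Brier score with the same bootstrap correction at a stated time. Six months would fit, as SAP 4.4.1.2 and 4.4.5.2 already report both survival endpoints there.
4. State that AIC decides if the measures disagree, among models fitted to the same patients. SAP 3.3 leaves missing values unreplaced by default, so a common analysis set has to be specified.

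The cost is a wording change in both documents, made before database freeze (SAP 1.6), and a few lines of code. There are two downsides. With 42 patients the slope will be imprecise, so it should be reported with that caution. Corrected performance will also look less favourable than the uncorrected figures.
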